will review all available safety and PK data collected from the first group of 4 subjects in each cohort. In order to identify the optimum dosage and dosing regimen in each age group, a maximum of 2 dosage/dosing regimen adjustments is assumed in either or both of the Cohorts 3 and 4. Subjects ≥ 6 months to ≤ 36 months of age can be enrolled in Cohort 5 after the completion of Cohort 3 and subjects ≥ 1 month and < 6 months can be enrolled in Cohort 5 after the completion of Cohort 4. Cohort 5 will be opened when either Cohort 3 or 4 is complete. Enrolment in Cohort 5 will continue until 24 evaluable subjects have received RV521 or placebo (2:1). The 4 subjects in the dose group that received the specified dose from each of Cohorts 3 and/or 4 will contribute to this overall total. Thus a minimum of 24 subjects and a maximum of 40 subjects (assuming 2 adjustments per age group) may be enrolled in Part B.

Part C (Multiple Dose, Parallel Group, Cohort 6)

Based on the analysis of the safety, PK, and antiviral data following the completion of Part B, Part C will commence to confirm the antiviral effects of the two dose levels of RV521 vs. placebo. Part C is a double-blind and placebo-controlled study, enrolling 1 cohort (Cohort 6) of up to 111 subjects (≥ 1 month to ≤ 36 months of age). After parent/legal guardian informed consent is obtained, and conditional to satisfactory fulfilment of all inclusion criteria and none of the exclusion criteria subjects will be randomised in a 1:1:1 ratio to receive RV521 at one of two dose levels (RV521 high or low dose) or matching placebo. Subjects will be followed for safety and tolerability, samples will be collected for PK levels, and clinical findings will be collected. Nasopharyngeal swabs will be obtained over the course of the study period to evaluate viral load, presence of other respiratory pathogens and the CCI [REDACTED].

Number of Subjects:

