Based on the analysis of the safety, PK, and antiviral data following the completion of Part B, Part C will commence to confirm the antiviral effects of the two dose levels of RV521 vs. placebo. The dose levels will be selected based on the paediatric PK model, and will target equivalent RV521 exposure levels between the two age groups (≥ 1 month to < 6 months and ≥ 6 months to ≤ 36 months). The DSMC will evaluate safety data at intervals specified in the DSMC Charter.

Part C will evaluate 111 subjects total (37 per treatment arm) aged ≥ 1 month to ≤ 36 months with an aim to have at least 34 evaluable subjects per treatment group. The primary endpoint will be the time-weighted average change from Baseline to Day 7 in RSV viral load measured in nasopharyngeal swabs by RT-qPCR comparing two dose levels of RV521 vs. placebo.

Secondary endpoints will assess the safety, and efficacy of two dose levels of RV521 vs. placebo. Dose levels in Part C will be selected following the analysis of PK data, tolerability and safety from Part B. Two doses (RV521 age group specific high dose and RV521 age group specific low dose) will be selected for inclusion in Part C. The high dose will be selected for each age group to target approximately 90% of subjects achieving the target trough concentration for efficacy (3x EC90), while not exceeding the upper safety limit, based on the paediatric PK model. The low dose will be selected such that the target trough level of 3xEC90 is achieved in approximately 75% of the subjects. The high dose may be the highest tolerated dose from Part B, or a higher twice daily dose of RV521, depending on the safety, tolerability and PK data from Part B.

Subjects in Part C will be stratified by age (≥ 1 to < 6 months of age vs. ≥ 6 months to ≤ 36 months of age) and randomised in a 1:1:1 ratio. Both age strata will be enrolled in parallel. To maintain the double-blind, subjects randomised to placebo will be allocated to low volume (to match the volume associated with the lowest tested dose of RV521) or the higher volume (to match the highest tested dose of RV521).

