11.1.3 Pharmacodynamic Variables

Pharmacodynamic variables include individual viral loads (by RT-qPCR) and/or CBIA if available at each sampling time point, percent change from baseline for 60 and 156 hours after first dose as well as other additional PD parameters may be also considered as PD endpoints.

For Parts B and C, the DAVG statistic (time-weighted average change in RSV viral load), for both total RSV viral load by RT-qPCR and RSV viral load by CBIA, will be calculated as:

$$DAVG = \frac{\sum_{i=a}^b 0.5 (Y_i + Y_{i+1}) (t_{i+1} - t_i)}{t_b - t_a}$$

Where Y_i is the change from baseline in \log_{10} RSV viral load at time point i , t is the actual time at the specified time point, a is the baseline assessment at Dosing Visit 1, and b is the last assessment on Follow up Day 7.

Pharmacodynamic parameters, including the viral load, AUC, and any other PD parameters which are derived, will be summarised by treatment (dose level). For Parts B and C, comparisons will be made between RV521 and placebo using analysis of covariance models. Data will be log transformed as appropriate.

The primary analysis in Part C will be the time-weighted average change in nasopharyngeal RSV viral load which will be calculated from baseline (Day of Randomisation) to Day 7 and compared across treatment groups. An analysis of the RSV viral load in the presence and absence of other known respiratory pathogens will be performed. This analysis will be outlined in the SAP.

Secondary virology endpoints derived from the RSV viral load as measured in nasopharyngeal swabs will include but are not limited to:

- Change from baseline in viral load (RT-qPCR and CBIA) at each time point
- Time to below viral load quantification limit (RT-qPCR and CBIA)

- Proportion of subjects with viral load below quantification limit (RT-qPCR and CBIA) at each timepoint throughout the study

CCI [REDACTED]
[REDACTED]
[REDACTED]
[REDACTED]
[REDACTED]

Note: the key analysis will pool subjects with both RSV A and RSV B. However, selected analyses will be repeated for the RSV A and RSV B subgroups separately.

Further details of the analyses will be provided in the SAP.

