11.1.7 Interim Analyses

No formal interim analyses will be conducted. Each of Parts A, B and C will be reported separately and no pooling of Parts will occur.

Following review of Part B, a decision will be made regarding the dose levels to be investigated in Part C.

Note: Part C data will be analysed separately to the Part B data. Data will not be combined across Parts B and C, and therefore, the analysis of Part B has no impact on the type I error.

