11.2 Determination of Sample Size

Because of the exploratory nature of the study, a formal sample size calculation has not been performed for Parts A and B. Twenty-four subjects enrolled in Part B and receiving RV521 or placebo (2:1) at the same dose level and according to the same dosing regimen for their specified age range group are expected to be sufficient to assess safety, PK, and antiviral data.

For an anti-viral effect (Part B), measured as a difference in viral load at a specific time point, and using data from the human challenge model (Study CCI [REDACTED]), 24 subjects split 16/8 would have 69% power to identify a difference of 2 log units, 87% power for a difference of 2.5 log units and 96% power for a difference of 3 log units.

Estimates for total enrolment into Part C are based on the report by [Cunningham et al \(2021\)](#); an assumed time-weighted average change in RSV log₁₀ viral load from baseline to day 7 in the placebo group of -1.5 log₁₀ vp/ml, with a standard deviation of 1.25. A sample size of 34 per group will provide 90% power to detect at least 1 log₁₀ decrease in RV521 groups using a 2-sided significance level of 0.05. To account for potential drop outs, an additional 10% will be added to give group size of 37 (total 111 subjects randomised 1:1:1; 2 dose levels of RV-521 vs. placebo).

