## 6. General Aspects for Statistical Analysis

### 6.1. General Methods

- Unless otherwise specified, summaries for Part A will be presented by cohort, dose level and overall, summaries for Part B will be presented by cohort, treatment, dose level and overall, and summaries for Part C will be presented by treatment and overall.
- Unless otherwise specified, continuous variables will be summarised using the number of observations (n), mean, standard deviation (SD), median, minimum, and maximum. Means and medians will be presented with one more decimal than the observed values. SD values will be presented with 2 more decimals than the observed values.
- Unless otherwise stated, categorical variables will be summarised using number of observations (n), frequency and percentages of subjects.
- Presentations for PK data are described separately in Section 9. Presentations for PD data are described in Section 10.
- All relevant subject data will be included in listings. All subjects entered into the database will be included in subject data listings.
- All statistical testing will be 2-sided with an alpha level of 0.05, with no adjustment for multiple comparisons.
- For Part B, formal statistical testing will focus on the 24 subjects treated at the doses used in Cohort 5 that were identified in Cohorts 3 and 4. These 24 subjects comprise the whole of Cohort 5, plus the 4 subjects from each of Cohorts 3 and 4 that were randomized with the selected dose/placebo.
- Where there are multiple assessments at a given time point, only the results recorded on the scheduled time point page of the case report form (CRF) will be used for summarisation, unscheduled assessments will be listed only.

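### Part C compares two RV521 doses with one placebo arm on the primary endpoint, but neither document gives a success rule or test order; the SAP's no-adjustment rule, if carried over, gives about 9% two-sided family-wise error

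*SAP*

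**What the plan says.** **Design and primary endpoint.** Protocol 8.2 defines the Part C primary endpoint as DAVG to Day 7, "measured in nasopharyngeal swabs by RT-qPCR comparing two dose levels of RV521 vs. placebo". Protocol 11.2 sizes it as "total 111 subjects randomised 1:1:1; 2 dose levels of RV-521 vs. placebo", with 34 evaluable per group for 90% power to detect a 1 log10 "decrease in RV521 groups using a 2-sided significance level of 0.05" (SD 1.25), raised to 37 for dropout. The synopsis gives the purpose: "Part C will commence to confirm the antiviral effects of the two dose levels of RV521 vs. placebo".

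**Analysis of the primary endpoint.** Protocol 11.1.3 says only that the endpoint is "compared across treatment groups". It does not say whether one significant dose is enough, whether both are needed, or which is tested first. For time to resolution, by contrast, Protocol 11.1.5 sets each dose against placebo separately. The one remark on type I error, in Protocol 11.1.7, concerns keeping Parts B and C apart: "the analysis of Part B has no impact on the type I error".

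**Multiplicity.** SAP 6.1 states: "All statistical testing will be 2-sided with an alpha level of 0.05, with no adjustment for multiple comparisons". SAP 8 repeats this for clinical efficacy.

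**What the SAP takes Part C to be.** SAP 3.5, 3.8.1 and 3.9 describe one RV521 arm against placebo, 1:1, in about 120 subjects. SAP 4.4 lists clinical-course endpoints as primary and viral load as secondary. SAP 10.2.1 fits one RV521-versus-placebo contrast to DAVG. No SAP text covers a two-dose primary analysis.

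**Route for change.** Protocol 11.1 requires SAP amendments for Part C to be signed off before database lock and unblinding of that part.

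**The concern.** Two active arms share one placebo arm on one primary endpoint, so an ineffective drug has two chances of a nominally significant result. Nothing in the protocol controls or orders those two tests, and the one rule on file declines to adjust.

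Two things are at stake. The first is the error rate attached to a statement that Part C confirmed an antiviral effect. The second matters even if the drug works: with no agreed rule, a trial in which one dose reaches 0.05 and the other does not would be interpreted after unblinding. The protocol's power statement refers to the RV521 groups in the plural without saying whether 90% applies to each dose or to both.

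**Working it through.** **Inputs.** From Protocol 11.2: difference 1 log10, SD 1.25, two-sided 0.05, 90% power, 34 evaluable per group, 1:1:1.

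**1. Reproduce the stated sample size.**
- Normal formula: n = 2 × 1.25² × (1.960 + 1.282)² / 1² = 3.125 × 10.51 = 32.8, so 33.
- Exact two-sample t-test: power 0.8926 at 33 and 0.9015 at 34. The stated 34 is reproduced.
- Alternatives (normal formula): one-sided 0.05 needs 27. Splitting alpha to 0.025 per dose needs 3.125 × (2.241 + 1.282)² = 38.8, so 39. Neither gives 34.

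The sizing therefore uses a full two-sided 0.05 for one dose–placebo pair.

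**2. Family-wise error with both doses inactive and either dose sufficient.** With equal arms, each contrast has variance 2σ²/n. The shared placebo gives covariance σ²/n, so the correlation is 0.5. From the bivariate normal:
- P(at least one |Z| > 1.96) = 0.0907. Simulated three-arm t-tests at 34 per arm give 0.090.
- Had the tests been independent: 1 − 0.95² = 0.0975. The upper bound is 0.10.
- Counting only results in favour of RV521: 0.045, against 0.025 for one test.

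**3. Power when both doses lower DAVG by 1 log10.** The standard error of each contrast is 1.25 × √(2/34) = 0.303, so the expected statistic is 1/0.303 = 3.30. Simulation with pooled variance on 99 df gives:

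| Outcome | Probability |
|---|---|
| A given dose significant | 0.904 |
| Both significant | 0.839 |
| At least one (2 × 0.904 − 0.839) | 0.969 |
| Exactly one (0.969 − 0.839) | 0.130 |
| Low dose only (0.904 − 0.839) | 0.065 |

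**4. Options at 34 per arm.**
- *Fixed sequence, high then low, each at 0.05.* If the high dose is inactive, any false rejection must begin with that test, so the error is at most 5%. If only the low dose is inactive, a false rejection needs its own test to pass, again at most 5%. Power is 90% for the high dose and 84% for the low dose (both must be significant).
- *Bonferroni, 0.025 each.* Family-wise error 4.65%; power per dose about 84%.
- *Dunnett, about 0.027 each.* Power per dose about 85%.
- Holding 90% per dose under Bonferroni or Dunnett needs 39 evaluable per arm, or 39/0.9 = 43.3, so 44 randomised.

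**The case against.** The strongest objection is that no document actually plans two primary tests at 0.05 each without adjustment. That reading joins a three-arm protocol to an SAP written for a two-arm Part C in which viral load is secondary. The SAP's revision history describes v2.0 as prepared before the Part A analysis, Protocol 11.1.3 defers analysis detail to the SAP, and Protocol 11.1 provides for a Part C amendment. On this view the rule is unfinished, not wrongly chosen. This stands as to where the fault lies: the SAP does not cover the current Part C. It does not remove the gap in the documents as supplied.

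The 9% is also conditional. It needs both doses inactive and a rule that either dose suffices. If both had to succeed, or testing were ordered, the error would be at most 5%. That is correct. But requiring both doses lowers power to 84%, which does not match the stated 90%, so the choice of rule matters.

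A reader might infer a 9% chance of falsely claiming antiviral benefit. The documents do not support that. The 9% counts significant differences in either direction, including RV521 worse than placebo; false benefit is 4.5%.

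Finally, this is Phase 2, and Protocol 6.5 speaks of exploring effects further in Part C. Labelling both tests nominal would be a legitimate choice, but it would have to be stated, and it sits poorly with the synopsis's aim to confirm.

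**Conclusion.** The gap is real and should be closed before unblinding. The protocol sets two doses against one placebo arm on the primary endpoint, sized at an unadjusted 0.05 per dose, and neither document says what counts as success. Carrying over SAP 6.1 with either dose sufficient would give a two-sided family-wise error of about 9% rather than 5%, and a false-benefit rate of 4.5% rather than 2.5%. These figures assume equal arms, both doses inactive and normal-theory tests.

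The 90% power is per dose. If both doses achieve 1 log10 with SD 1.25, power for both is about 84%, and about one trial in eight (13%) would have only one significant dose and no agreed reading.

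It would go too far to say that the sponsor has settled on two unadjusted tests: the SAP rule was written for a different Part C. The trial stays valid; what is missing is a rule that costs little to add now and cannot credibly be chosen once results are known.

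**What to change.** In the Part C SAP amendment, before database lock and unblinding:

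1. Align Part C with the three-arm protocol: arms, allocation and stratification, sample size, DAVG to Day 7 as primary, and a model with a contrast for each dose against placebo.
2. For that endpoint, replace the SAP 6.1 rule with a fixed sequence: high dose versus placebo at two-sided 0.05, then low dose versus placebo at 0.05 only if the first is significant.
3. State that if a dose is dropped on the monitoring committee's advice (Protocol 8.4.1 allows for this), the remaining dose is tested at 0.05. This assumes that the decision rests on safety and PK, not on the viral-load comparison.
4. State that all other tests are nominal.

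In Protocol 11.2, say that 90% power is per dose and that power for both doses is about 84%.

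**Cost.** No extra patients and no loss of power for the high dose. The multiplicity rule is one paragraph; aligning the SAP is more work, but is needed anyway. If both doses work, the high dose still misses about 9.6% of the time (1 − 0.904), and the low dose is then descriptive only. In about 6.5% of trials that forgoes a low-dose result that would otherwise have been significant. Holm or Dunnett would avoid this dependence and is acceptable, at some cost in power per dose. An explicit exploratory label would also close the gap if the sponsor does not want a confirmatory claim.

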### 6.2. Key Definitions

Baseline will be defined as the last non-missing result before the first dose of IMP. For ECG baseline, only results from the central ECG machine will be considered.

Study day will be defined relative to Dosing Visit 1, which should be Study Day 1. For Part A, study day will be calculated as date of event-date of study medication administration+1 if the event is on or after Dosing Visit 1 and as date of event-date of study medication administration if the event is before Dosing Visit 1. For Parts B and C, study day will be calculated as date of event-date of randomisation+1 if the event is on or after the date of randomisation and as date of event-date of randomisation if the event is before the date of randomisation.

#### **6.4. Visit Windows**

Deviations from planned sampling windows will be assessed before database lock for the impact on PK analyses and may be excluded from time point summaries of PK concentrations. Actual time will be used for derivation of PK parameters.

Deviations from planned sampling windows will be assessed before database lock for the impact on PD analyses. Actual time will be used for derivation of PD parameters.

#### **6.5. Pooling of Centres**

No formal pooling of centres is planned. CCI [REDACTED]

#### **6.6. Subgroups**

For Study Part C, all tables for the primary efficacy endpoints of RSV-related signs and symptoms, RSV Clinical Scoring System score and supplemental oxygen use and all pharmacodynamics tables will be presented by the following subgroups:

- Duration of symptoms prior to randomisation: < 4 days or ≥ 4 days.
- Severity of illness at randomisation: RSV score < 9 (mild-moderate) or ≥ 9 (severe).
- Baseline RSV subtype by RT-qPCR (A or B or Both.)
- Presence or absence of other known respiratory pathogens at baseline.
- Age group (≥ 1 month to < 6 months or ≥ 6 months to ≤ 36 months at screening.)
- Other subgroups may also be presented.

This document is confidential.

## 7. Demographic, Other Baseline Characteristics and Medication

No formal statistical testing will be carried out on these data.

### 7.1. Subject Disposition and Withdrawals

Subject randomisation details will be listed for all subjects allocated to Study Parts B and C. Subject disposition will be listed for all subjects in the database.

For Part A, the number and percentage of subjects treated, completed and withdrawn, together with the reasons for withdrawal, will be summarised for all subjects in the database.

For Parts B and C, the number and percentage of subjects randomised, replaced, treated, completed and withdrawn, together with the reasons for withdrawal, will be summarised for all subjects in the database.

The number and percentage of subjects included, and reasons for exclusion, from each of the analysis populations will be summarised for each study part.

### 7.2. Demographics

Demographic data will be listed for all subjects.

Demographic data (age, sex, race, ethnicity) will be summarised descriptively. Age at screening (months) will be calculated as (date of screening – date of birth)\*12/365.25 and presented to 1 decimal place.

Demographics will be summarised for the Safety, mITT and PK Populations.

### 7.3. Medical History and Concomitant Diseases

Relevant medical history, including surgical history, will be recorded on the CRF. The study disease (RSV LRTI) will not be entered as a medical history record.

Medical coding will use Medical Dictionary for Regulatory Activities (MedDRA) Version 22.1 for prior and concomitant diseases.

Medical history will be summarised by body system, as provided on the CRF, and preferred term (PT), as coded, using summary statistics for categorical data for the Safety Population, and sorted alphabetically by body system and PT.

Medical history data will be listed for all subjects with medical history and presented by record number.

### 7.4. Other Baseline Characteristics

CCI [REDACTED]  
[REDACTED]  
[REDACTED] For Parts B and C, the number and percentage of subjects that only have RSV and the number and percentage of subjects who also have other respiratory pathogens will be summarised for the Safety, mITT and PK Populations.

RSV diagnostic test details and CCI [REDACTED] results from the central laboratory will be listed for all subjects. Subjects for whom central laboratory results did not match the RSV diagnostic test result will be flagged in the RSV diagnostic test data listing.

This document is confidential.

## 7.5. Medication

All prior medication taken within 14 days prior to the study and all concomitant medication taken during the study will be documented in the CRF.

Medications will be coded using the World Health Organisation (WHO) Drug dictionary, WHODrug Global B3 Sept 2019. Prior and concomitant medications separately will be summarised by anatomical main group, therapeutic subgroup and preferred name for the Safety Population. Tables will be sorted by descending incidence of anatomical main group, then alphabetical within therapeutic subgroup and preferred name.

In order to classify medications documented on the Prior and Concomitant Medications CRF as prior or concomitant, missing and partial medication dates will be handled as follows:

Missing medication start dates likely to be after the date of first dose of IMP will be imputed as the date of first dose of IMP.

Missing end dates will be imputed as the date of last contact.

Incomplete medication start dates will be imputed using the earliest possible date implied by the portions of the date provided. If only the year is provided, January 1st of that year will be imputed as the start date. If the month and year are provided, the 1st day of the provided month/year will be imputed as the start date.

Incomplete medication end dates will be imputed using the latest possible date implied by the portions of the date provided. If only the year is provided, December 31st of that year will be imputed as the end date. If the month and year are provided, the last day of the provided month/year will be imputed as the end date. If any imputed end date would be after the subject's date of last contact, then the medication end date will be imputed as the date of last contact.

Prior and concomitant medications will be listed together for all subjects with medications with prior and concomitant medications flagged. The data listing will be sorted by start date, end date, Anatomical Main Group, Therapeutic Subgroup, Preferred Name and Verbatim Term.

